An innovative high strength, lithium disilicate ceramic material is reported to offer a more efficient fabrication process resulting in a similar esthetic and high strength crown. Lithium Disilicate Quartz (Ivoclar Vivadent) is a glass ceramic with crystalline phases of lithium disilicate and quartz.

Current glass ceramic materials have a recommended minimum thickness to maintain the maximum strength potential of the material. An occlusal thickness of 1.5 mm is generally recommended. This can be a challenge to achieve in the posterior of the mouth with teeth with limited clinical crown height. In addition, the glass ceramic material should be adhesively bonded to ensure maximum strength of the restoration. Lithium Disilicate Quartz offers an alternative high strength ceramic that may allow a more conservative occlusal reduction resulting in a crown thickness of 1.2 mm, equitable to the recommendation for full contour zirconia crowns. The material may also be sufficiently strong to allow for conventional cementation in addition to adhesive bonding.

Current high strength materials have not been embraced for partial coverage restorations due to the lengthy post-milling firing process. Lithium Disilicate Quartz may also offer a more clinical efficient process to fabricate partial coverage restorations since it does not require post-milling crystallization.

It is the intent of this investigation to evaluate the clinical application and performance of the new high strength, lithium disilicate quartz material for CAD/CAM-generated chair-side crown applications.

5 Summary of Objectives and Design

This investigation will be a randomized, prospective, longitudinal clinical trial to study the clinical performance of a new monolithic, high strength precrystallized lithium disilicate material for chairside CAD/CAM crowns. The restorations will be evaluated for a period of five years.

6 Specific Aims

The specific aims of this project are:

1. Evaluate the short-term post-operative sensitivity associated with cementation techniques using a self-adhesive, self-curing resin cement and a total etch/universal bonding agent with a dual-cured resin cement.
2. Evaluate the resistance to material chipping and fracture of reduced thickness high strength precrystallized lithium disilicate CAD/CAM crowns.

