3. Evaluate the longitudinal clinical performance of precrystallized lithium disilicate crowns over five years of clinical service. The crowns will be evaluated with modified FDI criteria for maintaining their esthetic, functional and biological properties.

7 Research Plan: Methods and Materials

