7.2 Study Size

There will be a maximum total of 80 monolithic, high strength precrystallized lithium disilicate crowns (Quartz by Ivoclar Vivadent). There will be 2 groups of 40 crowns differentiated by occlusal thickness and type of cement.

- Group 1 = occlusal thickness of 1.5 mm delivered with a self-adhesive, self-curing resin cement (SpeedCem Plus/Ivoclar).
- Group 2 = occlusal thickness of 1.2 mm delivered with Adhese Universal Adhesive in total etch mode with a dual cure resin cement (Variolink Esthetic by Ivoclar Vivadent).

The study will be a randomized, longitudinal clinical study with the outcome data to be benchmarked against published results of other chairside CAD/CAM materials.

8 Data Collection

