8.2 Clinical Evaluation

Two independent evaluators will examine all crowns in the study. Clinical evaluations will be made at baseline, six months, one year, two years, three years, four years, and five years using written criteria based on FDI criteria (Hickel et al., 2007 and 2010) (see Appendix for criteria description). Disagreements in evaluations will be discussed between the evaluators and a consensus judgment will be reached and recorded for every criteria.

Intraoral digital color pictures at a 1:1.5 magnification will be taken to document pre-operative, cavity preparation, and post-operative conditions. Facial and occlusal views of the tooth will be documented for both the pre-operative and post-operative conditions including occlusal contacts.

A post-cementation quadrant optical scan (CEREC PrimeScan) will be made of each test restoration at each recall visit. The scan will include the quadrant with the test crown, the opposing quadrant and buccal bite.

Bite-wing radiographs (BWXR) of each test tooth will be reviewed at the three-year recall. A new BWXR will be taken at the recall appointment at no cost to the patient if BWXR dated within 6 months of the three-year recall is not available for review. The use of

radiographs in the study is in compliance with the standard of care for ensuring and maintaining the health of the tooth during treatment and not for research-specific reasons.

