8.3 Data Management

Case Report Form (CRF)

Castor EDC is a cloud-based Electronic Data Capture (EDC) platform which will be used to collect data. All changes are tracked by an audit trail. The pictures are stored locally at the University of Michigan. After entering data by a study coordinator the data will be reviewed and approved by the principal investigator

9 Statistical Analysis

After the clinical evaluation data is collected for baseline and each recall, the clinical ratings will be entered into a statistical management program and appropriate non-parametric tests will be run to verify significant differences. Each criterion-referenced category will be analyzed independently. At any given time period, significant differences in clinical evaluation ratings will be determined.

10 Project Time Line

The recruitment of patients and clinical placement of restorations will begin immediately upon approval and funding of the project. It is anticipated to take 10 months to recruit and deliver the restorations required for the study. The 1-year recall will occur in the second year of the study, and similarly for future recalls in that the 2-year recall will occur in the third year of the study and continuing. This will result in a total time of 6 years required to place and complete the 5-year recall of the restorations with an additional 9 months needed to complete the data analysis and final report for the project. Additional recall periods beyond the 5 years may also take place following approval by Ivoclar Vivadent.

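### Section 9 plans significance tests of ratings but no cumulative chip/fracture estimate with a confidence interval, so Aim 2 and the Section 7.2 benchmarking have no planned statistic that can answer them

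*Combined protocol and SAP*

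**What the plan says.** Section 9 (Statistical Analysis) is the only analysis text in the combined protocol and SAP as available. It puts the ratings from baseline and each recall through non-parametric tests that it does not name, and adds "Each criterion-referenced category will be analyzed independently" and "At any given time period, significant differences in clinical evaluation ratings will be determined". It names no estimate, confidence interval or chip/fracture endpoint, and no rule for a crown that has been removed or replaced. It does not say which groups the tests compare.

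Other sections set what the analysis has to deliver:

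- Section 6, Aim 2: "Evaluate the resistance to material chipping and fracture of reduced thickness high strength precrystallized lithium disilicate CAD/CAM crowns".
- Section 6, Aim 3: "Evaluate the longitudinal clinical performance of precrystallized lithium disilicate crowns over five years of clinical service".
- Section 7.2: the study has its "outcome data to be benchmarked against published results of other chairside CAD/CAM materials".
- Section 5: "The restorations will be evaluated for a period of five years".
- Section 8.2: "Clinical evaluations will be made at baseline, six months, one year, two years, three years, four years, and five years".

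Aim 2 gives no time point, so the five-year horizon used here is inferred from Section 5 and Aim 3. For the rating criteria, Section 8.2 refers the reader elsewhere ("see Appendix for criteria description"). That appendix and the content of the CRF are not in the text available.

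**The concern.** Aim 2 is a question of how many crowns chip or fracture, and benchmarking sets such a figure beside a published one. Both need a rate with its uncertainty. A significance test of ratings gives neither, whatever its result.

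Two things are at stake. First, a report could state that no recall showed a significant difference and be read as evidence of fracture resistance, although the data might be compatible with a substantial failure rate. The event definition, the figure to be benchmarked and the published comparator would also remain open until the data had been seen. Second, if a failed crown is taken out and disappears from later comparisons, each later recall compares surviving crowns only and failures are spread thinly over six recalls. A real difference could then be missed.

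**Working it through.** **1. Inputs.** From the documents: 40 crowns in each of two groups, 80 at most (Section 7.2); six recalls after baseline (Section 8.2); up to two crowns per patient (Section 7.1). Not given, so assumed: two-sided 5% tests, 95% intervals, failure rates, the share of failed crowns removed, and loss to recall. Fisher's exact test stands in for the unnamed test, and binary failure for the ordinal ratings.

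**2. The plan's own figure.** 2 × 40 = 80 agrees. No error rate, power, event rate or target precision accompanies it, so there is nothing further to reproduce.

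**3. What a non-significant test shows.** For 0/40 v x/40, the two-sided Fisher p-value is 2 × C(40,x)/C(80,x).

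- x = 5: 2 × 658,008/24,040,016 = 0.055.
- x = 6: 2 × 3,838,380/300,500,200 = 0.026.

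Five fractures against none (12.5% v 0%) is therefore not significant, and six against none are needed.

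**4. What few or no failures show.** With no events in n crowns, the exact 95% upper limit is 1 − 0.025^(1/n).

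| Case | n | Upper limit |
|---|---|---|
| All crowns seen | 40 | 8.8% |
| 20% lost to recall (assumed) | 32 | 10.9% |
| Every patient has two crowns in one group, intra-patient correlation 0.3 (assumed) | 40/1.3 = 30.8 | 11.3% |
| Same, correlation 0.5 (assumed) | 40/1.5 = 26.7 | 12.9% |

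With events, the exact intervals are 0.6 to 16.9% for 2/40 (5.0%) and 2.8 to 23.7% for 4/40 (10.0%).

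**5. By-visit figure against cumulative figure.** Suppose one crown in a group of 40 fractures and leaves follow-up each year.

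- The share newly fractured among crowns seen runs from 1/40 = 2.5% to 1/36 = 2.8%. The cumulative share is 5/40 = 12.5%.
- If two further crowns are lost each year, the year-5 visit shows 1/28 = 3.6%. Kaplan-Meier gives 1 − (39/40)(36/37)(33/34)(30/31)(27/28) = 14.1% (95% CI 6.1 to 30.7%).

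These counts are invented to show the mechanism.

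**6. Effect of removal on the tests.** Assume five-year failure of 2% v 20%, constant hazard, independent crowns and no loss to recall. Each failed crown is scored as failed at its next recall. It is then removed and not carried forward with probability q; otherwise it keeps being scored as failed. Any-recall power is the chance that at least one of the six tests has p ≤ 0.05, unadjusted (200,000 simulated trials).

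| Failed crowns removed (q) | Year-5 power | Any-recall power |
|---|---|---|
| 0% | 64% | 66% |
| 25% | 59% | 62% |
| 50% | 46% | 53% |
| 100% | 5% | 16% |

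One test of cumulative failure has exact power 64%. This is the sum, over all pairs (a, b) with Fisher p ≤ 0.05, of Bin(a; 40, 0.02) × Bin(b; 40, 0.20).

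**The case against.** The strongest reply is that Section 9 is open rather than wrong. Its first sentence does not confine the tests to single visits, so a test across visits or a log-rank test is not excluded. The planned ratings could also be tabulated into failure counts later. This stands in part. A reader might infer that the plan permits by-visit tests only, and the wording does not go that far. But no other test is named, a log-rank test alone still gives no rate to benchmark, and a figure derived afterwards leaves the event, the removed-crown rule and the comparator unfixed.

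A reader might also infer that the planned tests will miss a real difference. The documents do not support that. They do not say what happens to removed crowns, and they give no failure rate or removal share. With none removed, any-recall testing has slightly more power than the cumulative test. Chipped crowns left in place continue to be scored and cause no loss.

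Nor does testing at every recall necessarily raise false positives. With 20% failure in both groups, the any-recall rate is 5.8% (none removed), 6.6% (half) and 2.8% (all), against 2.8% for the cumulative test. With 10% in both it is 2.5%, 2.1% and 0.4%, against 1.7%. The direction depends on the assumptions.

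Finally, Aim 2 concerns reduced-thickness crowns and names no comparison between groups, so the power figures are secondary to it. That is correct, and the point rests mainly on the one-group intervals.

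**Conclusion.** The point holds as an omission that should be fixed. Nothing in the text available plans a cumulative chip/fracture estimate or an interval, and Aim 2 and the benchmarking both need one. This part depends on no assumed failure rate, though the missing appendix and CRF limit it to the text available. Its practical size is the gap between non-significance and resistance at 40 crowns per group: a group with no failures at all remains compatible with a failure rate of 8.8%, or about 11 to 13% under the loss or clustering assumptions shown.

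The loss of power through removed crowns is conditional. Under the assumed rates it is a few points at 25% removal and becomes large only when many failed crowns are removed and not carried forward. By-visit FDI ratings suit Aim 3 and are not criticised here.

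**What to change.** Keep the by-visit FDI tables for Aim 3. For Aim 2 and the benchmark, add to Section 9:

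- **Endpoint.** One pre-defined endpoint, first chip or fracture, with the recall at which it is found.
- **Estimate.** Five-year cumulative incidence in each group with a 95% CI, by Kaplan-Meier or similar, censored at last recall and allowing for up to two crowns in a patient. If a group has no events, give an exact upper limit.
- **Removed crowns.** A crown removed or replaced because of chip or fracture counts as an event and stays in the cumulative figure.
- **Benchmark.** Fix the published value and its metric before analysis, and compare that value with the CI.
- **Group difference, if reported.** Give it with a CI and state that it reflects thickness and cement together, because the groups in Section 7.2 differ in both.

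The cost is a modest extra analysis and possibly a small CRF addition, with no extra visits or crowns. The downside is that the intervals will be visibly wide.

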7.1 Subjects

The patient population will be selected from current patients under clinical treatment at the University of Michigan Dental Clinics. Patients will be at least 18 years of age, of either gender, and of any ethnic background. Each patient should have at least one carious lesion or defective restoration to be restored on a maxillary or mandibular premolar or molar tooth. Each lesion or defective restoration should exhibit sufficient size or loss of tooth structure requiring a full crown restoration. The tooth should have at least one opposing tooth in occlusion and one adjacent tooth with an intact proximal contact. All teeth will test vital and be asymptomatic at the beginning of treatment. No more than two restorations will be placed per patient. If a patient presents with more than two acceptable teeth for the study, molar teeth will be included prior to premolar teeth. Exclusion criteria will include:

- Devital or sensitive teeth
- Teeth with prior endodontic treatment of any kind
- Teeth with a history of direct or indirect pulp capping procedures
- Patients with significant untreated dental disease to include periodontitis and/or rampant caries
- Women who self-report that they are possibly pregnant, pregnant, or lactating, as elective dental treatment is not indicated at these times
- Patients with a self-reported past history of allergies to the materials to be used in the study including composite resin cements or ceramic restorative materials
- Patients unable to return for the recall appointments

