8.1 Post-Operative Sensitivity

To evaluate the immediate post-operative sensitivity, patients will be contacted by telephone once a week after the initial appointment for four weeks or until the restoration is reported asymptomatic. A criterion-referenced rating scale will be used to measure sensitivity. The phone interview will be used as a follow-up procedure to minimize recall loss as the patient is not required to return to the clinic. During the phone interview a criterion-referenced rating will be made of functional tooth sensitivity using the following scale. Patients will only be asked to return for an evaluation if they are having continued discomfort or any indication of premature occlusal contact.

Sensitivity Criteria:

- 1= No sensitivity is experienced at anytime
- 2= Slight sensitivity is experienced occasionally but it is not uncomfortable
- 3= Moderate sensitivity is experienced intermittently and it is noticeably uncomfortable
- 4= Severe discomfort is noted routinely with cold or pressure stimulation

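### Section 9 tests ratings recall by recall and never adds up failures, so replaced crowns can drop out and later ratings can hide or reverse a group difference in failure

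*Combined protocol and SAP*

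**What the plan says.** Section 7.2 sets the size: "There will be a maximum total of 80 monolithic, high strength precrystallized lithium disilicate crowns", and "There will be 2 groups of 40 crowns differentiated by occlusal thickness and type of cement". Section 7.1 adds that "No more than two restorations will be placed per patient".

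Two of the aims in Section 6 depend on crowns failing or lasting. Aim 2 is "Evaluate the resistance to material chipping and fracture of reduced thickness high strength precrystallized lithium disilicate CAD/CAM crowns". Aim 3 is "Evaluate the longitudinal clinical performance of precrystallized lithium disilicate crowns over five years of clinical service". Section 8.2 fixes the visits: "Clinical evaluations will be made at baseline, six months, one year, two years, three years, four years, and five years". It has two evaluators examine every study crown, but does not say what is recorded once a crown has gone.

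Section 9 is the whole analysis plan. It calls for unnamed non-parametric tests, analyses each category on its own, and states: "At any given time period, significant differences in clinical evaluation ratings will be determined". It contains no definition of failure, no cumulative or time-to-failure analysis and no missing-data rule.

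For Aim 1, Section 8.1 has weekly telephone scores from 1 (none) to 4 (severe), stopping at four weeks or earlier if symptoms have gone. It adds: "Patients will only be asked to return for an evaluation if they are having continued discomfort or any indication of premature occlusal contact". It does not say which summary of the weekly scores is compared.

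**The concern.** Fracture is a named outcome (Aim 2) and also an event that can take a crown out of the mouth. Debonding, caries and pulpal disease can do the same. Once a crown is removed or replaced, it has no rating of its own at later recalls: the value is either blank or belongs to a different crown. If ratings are tested afresh at each recall and failures are never added up, a failure counts at most at the recall where it is found. The five-year ratings, which bear directly on Aim 3, then describe the crowns that lasted. The group that lost more crowns can look the same as the other group, or better if its weaker crowns are the ones that went.

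The telephone scale has a milder form of the same problem. Because calls stop when the tooth is symptom-free, a tooth that scored 4 and then settled ends at 1, as does a tooth that was never sensitive. If the last score were compared, early sensitivity would disappear from Aim 1.

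**Working it through.** **The plan's own figure.** 2 × 40 = 80 crowns, which agrees with Section 7.2. The documents give no alpha, power, failure rate or dropout, so no sample-size calculation can be reproduced. All failure counts below are assumptions. Follow-up is taken as complete apart from failures, and crowns are treated as independent although one patient may have two.

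**1. Cumulative failure against survivors' ratings at year 5.** With f failures of 40 in each group, the cumulative comparison is Fisher's exact test (two-sided) on f/40 in each group. For 8 v 1, nine failures are shared between two groups of 40. The hypergeometric probabilities are 0.0133 for an 8–1 split and 0.0012 for 9–0, so p = 2 × (0.0133 + 0.0012) = 0.029. If every surviving crown is graded 1, the year-5 ratings are identical in both groups.

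| Assumed failures | Percentages | Fisher p, cumulative | Survivors rated at year 5 |
|---|---|---|---|
| 8 v 1 | 20% v 2.5% | 0.029 | 32 v 39, all grade 1 |
| 7 v 1 | 17.5% v 2.5% | 0.057 | 33 v 39, all grade 1 |
| 8 v 2 | 20% v 5% | 0.087 | 32 v 38, all grade 1 |
| 4 v 1 | 10% v 2.5% | 0.36 | 36 v 39, all grade 1 |

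**2. Survivors who are not all perfect.** Take 2 v 8 failures, with about 80% of survivors at grade 1 and the rest at grade 2. That gives 30 ones and 8 twos (mean 46/38 = 1.21) against 26 ones and 6 twos (mean 38/32 = 1.19). Mann-Whitney p = 0.82. If failures are kept at an assumed worst grade of 5, the means are (46 + 10)/40 = 1.40 and (38 + 40)/40 = 1.95, with p = 0.21. Cumulative failure gives p = 0.087.

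**3. Reversal.** Keep 2 v 8 failures, but let the crowns that fail in the second group come mainly from those that would have been graded 2. Survivors at grade 1 are then 30/38 (79%) v 30/32 (94%). The group that failed four times as often looks better, with Mann-Whitney p = 0.08 in its favour.

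**4. Counting each failure only where it is found.** Spread the same 2 v 8 failures over the six recalls as 0, 0, 1, 0, 1, 0 and 1, 1, 2, 1, 2, 1, and remove each failed crown afterwards. Fisher p by recall is 1.0, 0.49, 0.61, 0.48, 0.60 and 0.46, against 0.087 when the failures are added up.

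**5. Sensitivity.** Suppose 4/40 v 12/40 teeth ever score 3 or more: Fisher p = 0.048. If nine of the twelve have settled to 1 by week 4, for whatever reason, the week-4 comparison is 4/40 v 3/40, p = 1.0.

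**The case against.** - **Silence is not a rule.** A reader might infer that the plan drops failed crowns, or that its scale has no terminal grade. The documents do not support either reading. The rating criteria are in an Appendix that is not in the available text, and it may contain a failure grade. Section 8.2 has all crowns examined, and a chipped or fractured crown still in place can be rated at the recall where it is found. This stands. It limits the point to removed or replaced crowns and to what happens after that recall. Criteria for grading a crown would not by themselves supply a cumulative analysis in Section 9.
- **Sensitivity.** A reader might infer that treated teeth are re-scored to 1. Section 8.1 describes a return for evaluation and no treatment. It names no final score, and earlier weekly scores remain on record. Section 9 also does not clearly cover telephone scores. All of this stands. What remains is that no summary score is named and that a last-score comparison would lose the earlier sensitivity.
- **Significance.** Of the four cases in the first table, only 8 v 1 falls below 0.05, so adding up failures does not guarantee a significant result. This is correct. The argument concerns what is being compared, not whether p crosses a threshold.
- **Direction.** The effect is not always towards no difference, since example 3 reverses it. The claim is therefore that a difference can be hidden or reversed.

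**Conclusion.** The point holds for crowns that are removed or replaced. Followed as written, Section 9 allows later recalls to compare surviving crowns, and it contains no analysis that accumulates failures for Aims 2 and 3. The possible size runs from a masked 10% v 2.5% (p = 0.36 even when added up) to a masked 20% v 2.5% (p = 0.029), and a reversal is possible. These figures rest on assumed counts, otherwise complete follow-up and independent crowns. How often it matters depends on failure rates that the documents do not give. Because Section 7.2 changes thickness and cement together, any difference in failure belongs to the combination and not to thickness alone. For Aim 1 the gap is smaller: an unnamed summary score that one phrase would settle. The change should be made before group results are compared, since a rule chosen afterwards could decide the conclusion.

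**What to change.** **Section 9, failure.** Define failure as a crown removed or replaced for a restoration-related or tooth-related cause, or graded as failed under the Appendix criteria. Compare the groups on cumulative failure by each recall, or on time to failure. Keep every crown placed in its group, censor crowns lost without failure, and allow for two crowns in one patient, for example with a patient-clustered variance.

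**Section 9, ratings.** At visits after a failure, keep the worst grade for the criterion that caused it and show how many grades are carried forward. Label the other criteria as ratings of surviving crowns, with the number rated in each group. A worst grade on the causal criterion alone would leave survivor comparisons on all the others, so the cumulative analysis has to carry the failure question.

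**Section 8.1.** Make the Aim 1 comparison the worst score over the four weeks. Flag scores recorded after any intervention, but keep them in the main result.

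**Cost.** A few sentences in Sections 8.1 and 9, the date and cause of each failure, and one check box per call. The small downside is that later ratings mix observed and carried-forward grades, which is why the counts must be shown. Nothing here changes clinical care.
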